4.5 Participant Management and Follow-up

All participants will be assigned a behavioral coach. This individual will provide all of the telephone coaching sessions, and will be the primary point of contact. A separate study coordinator will be in contact with all participants to schedule each of the follow-up visits and, once scheduled, will email participants a separate link to complete surveys. Surveys can be completed either at home or in-person during the follow-up assessments. During the final follow-up session at 6-months, participants will be administered an exit interview to collect information about their experience in the intervention, the components that they were assigned, and general feedback about the application. As mentioned in the IRB-approved Opt-IN consent form, all randomized participants are invited back at the conclusion of the study to an optional one-hour participant results session, in which study staff will overview study findings, and discuss study data and conclusions with participants.

4.5.1 Retention Strategies

At the outset of the intervention, participants will provide written and informed consent to be contacted by our research staff for the duration of their participation in the trial. Continued follow-up will be important for the collection of follow-up data. Our experience in previous clinical trials suggests that we are able to retain over 90% of the sample across all follow-up assessments. In our experience, establishing working relationships with participants, regardless of group assignment, is the single most important factor in enhancing retention. One technique commonly used is sending greeting cards such as birthday, holiday, or sympathy cards. Our research staff is well versed in this approach. Additionally, the study staff will monitor participant follow up and participation, will follow the missed contact protocol (see appendix) following corresponding scripts and will send a missed contact letter (see appendix) if the individual fails to answer a coaching call or return messages to schedule follow-up sessions. After missed contact, attempts to contact will be made no more than 6 times by phone and 4 times by email over the course of the 6 month enrollment of the participant unless contact is re-established by the participant. Both participants and locator persons may request no further contact be made and the research study personnel will cease attempts to contact at that time and document this request in the study file.

Participants will receive a financial incentive for attending each of the follow-up visits. Participants will receive \$20 for completing each in-person assessment for a total of up to \$40, and their downtown Chicago parking will be reimbursed.

4.5.2 Strategies to Promote Adherence

Two forms of participant adherence are necessary in this intervention and include **assessment adherence**, and **behavior change adherence** (described below).

Assessment Adherence (needed for all groups) requires: a) reliable and accurate intermittent self-reporting of outcomes (dietary intake, mediators), and b) attendance at in-person assessment sessions.

Behavior Change Adherence requires adherence with following behavioral prescriptions. Several protocol features will enhance adherence for all groups. Participants are offered small

financial incentives contingent on assessment adherence at 3 months and 6 months. All participants will be well trained on dietary intake recording, food preparation methods, etc. to support collection of accurate baseline data prior to randomization, as well as to follow-up assessments. Automatic wireless uploading of data will enable rapid detection and outreach regarding skipped recording or obvious errors.

Additional procedures to support adherence to behavioral prescriptions include: a) visual goal thermometers to provide cues about intake and expenditure relative to targets; b) ability to access smartphone diet and activity information throughout the day to assist in making behavioral choices; c) use of stepped goals to facilitate incremental attainment of targets; d) use of self-monitoring, provision of personalized feedback, and tailored behavioral recommendations; and e) provision of sustained counselor support via scheduled telephone and e-mail contact throughout the protocol.

4.6 Safety Monitoring / Adverse Event Reporting

All participants will be in contact with behavioral coaches on a regular basis. In the case of any adverse events that may arise during the study, OPT-IN staff will immediately consult with the PI and follow all necessary reporting procedures. Any participant that experiences an adverse medical event or refuses treatment following an elevated blood pressure (>180/120) during the study, which makes it no longer medically safe for the individual to participate in the OPT-IN intervention, will be withdrawn from the study. These cases will be promptly reported to the IRB and our standing DSMB committee.

4.6.1 Potential Risks

The risks of participating in OPT-IN are minimal. 1) Participants may experience muscle soreness or pain from walking on the treadmill and increasing physical activity. Participants will be encouraged to stretch and always exercise in a safe and reasonable manner. Participants will be instructed to contact their coach immediately if they have any pain from exercising. 2) Participants may experience an injury as a result of their physical activity. Participants are encouraged to stop exercising immediately if at any time they are injured. 3) Participants may experience feelings of hunger and deprivation from decreasing calorie and fat intake. 4) Some of the questions asked may be upsetting or may makes participants feel uncomfortable answering them.

Risks for the Buddy participants may include another “Buddy” in a webinar revealing personal information about another Buddy. The study staff will take all precautions to keep personal information confidential, but the study cannot fully control what the members of the webinar do with the information that is revealed to them.

4.6.2 Surveillance and Reporting Procedures

The study coordinator will assess for any adverse events at each of the study visits. These events will be communicated to the Safety Officer within 7 days for determination of level of seriousness and relationship with the intervention. For each event, a form provided by the Northwestern University IRB will be completed. This form will then be reviewed and signed by [name] (Principal Investigator), and submitted to the local IRB. A copy of this form will also be forwarded to the Safety Officer for review and confirmation as to whether the event appears to be related to the intervention.

4.6.3 Safety Monitoring Plan

Data Safety Monitoring Plan (DSMP). The NIH statement "NIH Policy for Data and Safety Monitoring" was modified by NIH Notice OD-00-018 dated June 5, 2000, entitled Further Guidance on a Data and Safety Monitoring for Phase I and Phase II Trials, and states "For many

phase I and phase II trials, independent DSMBs may not be necessary or appropriate when the intervention is low risk. Continuous, close monitoring by the study investigator may be an adequate and appropriate format for monitoring.” We believe that this modification applies to the present proposal, since the study interventions and assessment procedures pose a low level of risk, and because this trial is equivalent to a Phase II study (e.g. single site). However, we recognize that DSMBs can also be of considerable help and guidance to the Co-PIs both in preserving the safety of patients and data, and in the general conduct of the study. Therefore, we propose to have a DSMB that is partially independent, and is comprised of a broad range of specialists who can oversee the study and offer guidance to the PI. The Data Safety Monitoring Board (DSMB) will have two voting members and two non-voting members. It will be chaired by [name]., Research Assistant Professor at Northwestern University. [name] will be a voting member. He has no other role on this study and is therefore independent. [name], a biostatistician in the Department of Preventive Medicine at Northwestern who is independent of the study will also be a voting member of the DSMB. Drs. [name] (Co-PI) and [name] (Co-PI) and [name], project statistician, will be non-voting members of the DSMB. They will attend all meetings primarily to provide and receive information. The DSMB will convene in person or by telephone at least every six months. They will review all adverse events as well as data on study recruitment and retention. Study staff are instructed to inform the DSMB immediately if any participant is experiencing serious medical or psychiatric deterioration that is thought to be study-related. The appropriate member of the DSMB will evaluate or oversee the evaluation of the participant. If the patient is determined to have deteriorated, the patient will be referred for appropriate treatment and, if necessary, discontinued from the study protocol. Northwestern University’s Office for the Protection of Research Subjects and IRB will be contacted immediately at all serious adverse events that are thought to be study-related. Reports will be written immediately for all events deemed significant by the Northwestern University IRB and reports will be provided to all DSMB members. DSMB members may also be called upon for advice in managing such problems. Reports from DSMB meetings will be given to the Northwestern University IRB and the NIH program officer. If there are any suspected signs of consistent adverse events, we will ask the Northwestern University IRB to assist in the appointment of an outside monitor to review data and protocols. The biostatistician and project coordinator will also perform all necessary checks and controls to ensure the reliability and validity of the data, including monitoring data collection and collection procedures, data storage, data management, and data analysis. [name] will provide the DSMB with a data report at each meeting.

4.6.4 Rules for Participant Termination

Participants may withdraw from the study at any time. Permission will be sought to continue to collect outcome data for use in the analysis.

5 Statistical Considerations and Data Analytic Plan

The effects of the five individual intervention components will be examined by means of a factorial experiment (see Table 3) involving the following factors: 1) Number of telephone coaching Sessions (12 vs. 24); 2) PCP receives reports (no vs. yes); 3) Text messaging (not provided vs. provided); 4) Meal replacements (recommended vs. not recommended); 5) Buddy Training (not provided vs. provided). Although each of these intervention components has been part of a bundled weight loss intervention previously found to be successful, none of those studies was designed to estimate the impact of any individual component.

We initially chose a factorial experimental design with 16 experimental conditions, and have been conducting this experiment. We recently decided that a complete factorial experiment, obtained by adding 16 more experimental conditions to the design for a total of 32, would have statistical properties that better suit our scientific objectives. Table 3 shows all 32 experimental conditions, indicating which ones we have been running to date (not shaded) and which ones we propose to run (shaded).

Please note that we are not introducing any new experimental treatments; the conditions are merely different permutations of the same five individual components.

The statistical analysis plan for the data remains essentially the same as was originally submitted. The only difference is that in the previous design there was some aliasing of effects that does not occur in the new design.

Table 3 Experimental Conditions in Opt-In Design, with New Conditions Shaded				
Coaching Sessions	Report to PCP	Text Messages	Meal Replace	Buddy Training
12	NO	NO	NO	NO
12	NO	NO	NO	YES
12	NO	NO	YES	NO
12	NO	NO	YES	YES
12	NO	YES	NO	NO
12	NO	YES	NO	YES
12	NO	YES	YES	NO
12	NO	YES	YES	YES
12	YES	NO	NO	NO
12	YES	NO	NO	YES
12	YES	NO	YES	NO
12	YES	NO	YES	YES
12	YES	YES	NO	NO
12	YES	YES	NO	YES
12	YES	YES	YES	NO
12	YES	YES	YES	YES
24	NO	NO	NO	NO
24	NO	NO	NO	YES
24	NO	NO	YES	NO
24	NO	YES	NO	NO

24	NO	YES	NO	YES
24	NO	YES	YES	NO
24	NO	YES	YES	YES
24	YES	NO	NO	NO
24	YES	NO	NO	YES
24	YES	NO	YES	NO
24	YES	NO	YES	YES
24	YES	YES	NO	NO
24	YES	YES	NO	YES
24	YES	YES	YES	NO
24	YES	YES	YES	YES

All of the estimated main effects and interactions will be based on all 32 experimental conditions. For example, the main effect of Number of Coaching Sessions will be estimated by comparing the mean of Experimental Conditions with 12 coaching calls in Table 3 vs. the mean of Experimental Conditions with 24 coaching calls. Similarly, the main effect of PCP report will be estimated by comparing the mean of Experimental Conditions having PCP progress reports sent vs. the mean of Experimental Conditions not having PCP progress reports sent. Note that in each case, all experimental subjects are included in the estimate. That is why factorial experiments can have small sample size/condition and still have excellent power if the overall sample size is sufficiently large.

Primary Aim 1 is to test for differences in weight by intervention components across the timepoints (baseline, 3- & 6-months), under an intent-to-treat basis, using linear mixed models. For each of the five components, we will determine whether there is a difference in change across time using baseline as the reference cell (i.e., 3-months vs baseline and 6-months vs baseline). From one perspective this is a main effect of each component on the pre-post difference. However, statistically these effects will be modeled as component by time interactions, with the 6-month outcome as the primary endpoint. We will also include two way interactions between components (e.g., Component 1 by Component 2 by time interaction). We note that (a) testing 2-way interactions between intervention components is extremely novel, as traditional RCTs are not capable of looking at these effects, and (b) because we will be using effect (-1,1) coding rather

than dummy (0,1) coding, the power for tests of main effects and interactions are identical for effects of identical size. We expect that testing these effects will be valuable, as we may find, e.g., that two intervention components each have independent main effects, but that when combined they offer no incremental effect. Our plan for dealing with such cases is elaborated below.

Primary Aim 2 is to make decisions about intervention components and component levels based on the factorial experiment results. We propose to use a modified version of a decision making approach frequently used in engineering (Wu & Hamada, 2000), which emphasizes main effects, using interactions as additional valuable information. This emphasis is consistent with our objective of identifying a set of components and component levels in which each component is making a detectable contribution to the overall effect, and any inactive components have been eliminated. We remind the reader that the mixed model analysis will be performed using effect coding, which will keep any covariances among main effects and interactions to a minimum. This makes it reasonable to start the decision making process by examining main effects, and then to consider interactions carefully in subsequent steps in the process. (Recall that our theoretical model does not predict any substantially-sized higher-order interactions, which is the basis for selection of the highly economical fractional factorial design. This Resolution V design enables examination of all two-way interactions.) The decision making process can be summarized as follows: Step 1: Initial tentative selection of components and component levels, consisting of identification of the components that show a significant main effect on the primary outcome variable, weight. If buddy training, recommended meal replacements, texting, or PCP report have a significant main effect, they will tentatively be selected for inclusion in the intervention. If there is a significant positive main effect of Number of Phone Coaching sessions, this is evidence that the more expensive level (24 sessions) performs better than the less expensive level (12 sessions), so it should be selected; otherwise, the less expensive level should be selected. Step 2: Consideration of interactions and final decision. Next we will examine interactions to look for any indication that we should consider reversing a decision made in Step 1. For example, suppose both Texting and PCP Report have significant main effects, so they were tentatively selected in Step 1. If there is a significant negative interaction between them, this means that the combined effect of Texting and PCP Report is less than the sum of the main effects. Suppose Texting has the larger main effect of the two. In that case we will start from the premise that Texting is selected, and then pose this question: When Texting is selected, *does PCP Report have a large enough incremental effect to justify its selection?* This question can be addressed by examining the simple effect of PCP Report when Texting is at the Yes level. Similar decision making logic will be used to examine all significant interactions that involve any components selected in Step 1 to arrive at the final decisions about selection of components and component levels. Step 3: Identifying the combination of components and levels that produces the largest effect that can be obtained for \$500 or less. If the costs associated with the combination of component and component levels selected in the process described above exceeds the upper limit of \$500, it will be necessary to consider less expensive versions of the intervention. Using as a starting point the set of components and component levels selected in Step 2, we will examine various scenarios in which we remove Yes/No components and change the levels of Either/Or components, and compute the expected outcome based on the regression parameters obtained in the statistical analysis to select the one with the largest expected effect that can be delivered for under \$500.

Secondary Aim (Mediation & Moderation). 1. Mediation analysis conducted on the data from a RCT enables the examination of the mediated effects of the intervention as a package. In contrast, we will be able to fit models specifying *which* intervention component is mediated by each putative mediator, where the putative mediators are (a) adherence (treatment attendance; diet, activity, and weight self-monitoring adherence), (b) supportive accountability (therapeutic alliance, autonomy support), (c) self-efficacy (diet, activity), (d) self-regulation (restraint,

disinhibition, autonomous motivation), (e) facilitation. We will test the mediation effects for significance using the general approach described in MacKinnon.⁴³ 2. Moderation analysis. To improve the field's understanding of differential response to individual intervention components we will conduct analyses separately for subgroups (e.g. men and women; different age and ethnic groups; different categories of BMI) to investigate whether certain intervention components are more effective or less effective in certain subgroups. We will also use latent class analysis to explore the data for latent subgroups, and will fit models predicting latent subgroup membership. The results will inform subsequent research aimed at developing interventions tailored to and optimized for these subgroups.

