3.5 Randomization Method

Randomization, stratified by gender, will be computer-generated using the method of randomly permuted blocks. Participants will be informed of their treatment assignment by telephone. Candidates who, when queried, indicate unwillingness to participate in any condition will not be randomized.

4 Study Procedures

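### The primary mixed model names no term for randomisation stage (before or after the move from 16 to 32 conditions); this biases nothing, but gives up a little precision if weight change differs between stages.

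*Combined protocol and SAP*

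**What the plan says.** Section 5 (Statistical Considerations and Data Analytic Plan) describes a change of design during recruitment: "We initially chose a factorial experimental design with 16 experimental conditions, and have been conducting this experiment". The complete factorial is "obtained by adding 16 more experimental conditions to the design for a total of 32". On the consequences for analysis it says "The statistical analysis plan for the data remains essentially the same as was originally submitted", and adds: "The only difference is that in the previous design there was some aliasing of effects that does not occur in the new design".

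The two groups of participants are then pooled: "All of the estimated main effects and interactions will be based on all 32 experimental conditions", and "Note that in each case, all experimental subjects are included in the estimate". The primary analysis is a linear mixed model for weight at baseline, 3 and 6 months. Of the component effects the plan says that "statistically these effects will be modeled as component by time interactions, with the 6-month outcome as the primary endpoint". It adds two-way component interactions, also by time. No stage, period or enrolment-date term is named.

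Section 3.5 reads: "Randomization, stratified by gender, will be computer-generated using the method of randomly permuted blocks". Gender is the only stratification factor given.

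**The concern.** Participants enrolled before the change could be assigned to only half of the final 32 conditions; those enrolled later were assigned under the expanded design. Stage is therefore a grouping within which randomisation took place, much as gender is. A model normally reflects the groups within which participants were randomised, because differences between those groups have already been balanced out by design and need not count as noise.

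Recruitment runs for a little over three years (Section 7.1), so some drift in average weight loss is possible, for example through changes in who enrols or in coaching staff. The documents give no evidence that drift occurred. If it did, it would enter the residual and the reported standard errors would be larger than the design warrants. Section 5 selects components in its Step 1 on statistical significance, and the sample size leaves no slack above 80% power, so precision has some bearing on decisions.

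**Working it through.** **Inputs.** From Section 5.2: SD of weight change 4 kg, taken from a cited outside study; target difference 1 kg (effect size 0.25); 560 randomised; 10% attrition; 504 evaluable, 252 per level of each component; 80% power, two-sided. Alpha is not stated there; 0.05 is assumed. The share p randomised before the change and the stage difference d in mean 6-month weight change are not given, so both are varied.

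**1. The plan's own figure.** SE of a main effect = 4 × √(2/252) = 0.356 kg. Power = Φ(1/0.356 − 1.96) = 80.1%. Sample size: 504/0.90 = 560. The stated figures reproduce.

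**2. Is anything biased?** A five-factor, 16-run, Resolution V half fraction has defining relation I = ±ABCDE. Stage was correlated with each of the 5 main effects and 10 two-way products, for an initial half fraction followed either by the other 16 conditions only or by all 32 (Section 5 leaves this open). Every correlation was zero. Stage is correlated only with the five-way product (1.0 if the later stage uses only the new 16, 0.5 if it uses all 32), and the planned model does not name that term. In simulation (504 participants, 2,000 runs per case, 50:50 split, true effect 1 kg, stage differences of 0 to 4 kg) the mean estimate was 0.98 to 1.01 kg with or without a stage term.

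**3. Size of the precision loss.** Omitting stage gives residual SD = √(16 + p(1−p)d²).

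| Split | d (kg) | Residual SD (kg) | Reported SE larger by | Power |
|---|---|---|---|---|
| any | 0 | 4.000 | 0% | 80.1% |
| 50:50 | 0.5 | 4.008 | 0.2% | 80.0% |
| 50:50 | 1 | 4.031 | 0.8% | 79.5% |
| 50:50 | 2 | 4.123 | 3.1% | 77.7% |
| 50:50 | 3 | 4.272 | 6.8% | 74.8% |
| 25:75 | 1 | 4.023 | 0.6% | 79.7% |
| 25:75 | 2 | 4.093 | 2.3% | 78.3% |

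For example, at 50:50 and d = 2: √(16 + 0.25 × 4) = 4.123, and 4.123/4 = 1.031.

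These powers put the inflated SD into the whole calculation, so they slightly overstate the loss. When components are balanced within stage, the estimate itself does not vary more; only its reported SE grows. Power is then Φ(1/0.356 − 1.96 × SD/4), which at 50:50 gives 79.7% for 1 kg, 78.4% for 2 kg and 73.1% for 4 kg. The simulation agrees: at 4 kg, power was about 73% without the term and 80–81% with it, and the spread of the estimates was the same.

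**4. Can component effects be compared between stages?** SE of the difference = 2 × 4/√(504 × p(1−p)). At 50:50 this is 8/√126 = 0.71 kg (95% interval about ±1.4 kg); at 20:80 it is 8/√80.6 = 0.89 kg (about ±1.75 kg). Both intervals are wider than the 1 kg the trial is designed to detect.

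**The case against.** The strongest objection is that almost nothing is at stake. Each component is assigned 1:1 under either list, so valid tests do not need a stage term, and omitting it makes the tests slightly conservative. A stage difference as large as the trial's whole target effect costs about half a point of power, and a five-point loss needs roughly 3 kg. The 4 kg SD may already contain some between-period variation. A two-level term would not capture drift within a stage. Gender, the one named stratification factor, is not listed in the model description either, so the text may simply not list covariates. All of this stands, and it keeps the point minor.

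The authors did not ignore the change. Section 5 reports it, says that no new treatments are introduced, and names the removal of aliasing as its consequence. What is missing is one covariate.

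A reader might infer that pooling the stages biases the component effects, or that every planned interval is wider than it should be. The documents support neither. Stage is orthogonal to all modelled component terms, and intervals widen only if the stages differ, of which there is no evidence. Nor does anything in the documents show that outcome data prompted the change.

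The objection to reporting component effects by stage also stands. Within the initial half fraction each main effect is fully aliased with a four-way interaction. If the later stage used only the new 16 conditions, the alias has the opposite sign; if it used all 32, there is none. The two sets of estimates measure the same thing only if four-way interactions are negligible. Section 5 expects no substantial higher-order interactions, but the comparison would rest on that, and it is too imprecise to show agreement.

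**Conclusion.** The point holds as a small matter of efficiency. Two randomisation stages are pooled and the primary model names no term for them. At an assumed 50:50 split and SD of 4 kg, the reported standard error is about 0.8% larger for a 1 kg stage difference and 3% larger for 2 kg, with power 79.5% and 77.7% against 80.1%; the loss is smaller at uneven splits and zero if the stages do not differ. Orthogonality is exact for completed blocks and very nearly so otherwise. If the later stage used only the 16 new conditions, stage is fully aliased with the five-way interaction, which does no harm while the model stops at two-way component terms. Aliasing among the component effects themselves is a separate matter that a stage term neither causes nor cures.

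**What to change.** Add one sentence to Section 5: the primary mixed model includes randomisation stage (before or after the change of design, known from the randomisation date) and stage-by-time as fixed effects. With three time points this costs about three degrees of freedom (one for stage, two for stage-by-time) with about 504 participants expected at 6 months. Settle it before outcomes are analysed, so that the term cannot look data-driven. It would also help to state how many participants were randomised before the change and whether later participants were assigned among all 32 conditions or only the added 16.

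Do not plan component estimates by stage. If they are shown, label them purely descriptive, give them no role in component selection, and state both caveats: the aliasing with four-way interactions within the initial half fraction, and a stage-contrast SE of about 0.7 to 0.9 kg, which cannot establish agreement.
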